For Aims 1 and 2, we will obtain approval from the Minneapolis VA Health Care System's (VAHCS) Institutional Review Board (IRB) for all research activities involving human subjects. We will also seek union approval prior to recruiting providers for Aim 1 activities. With the exception of the providers being interviewed as part of Aim 1, the project will not involve any other non-Veteran participants.

1. Human Subjects Involvement and Characteristics

Aim 1. We aim to enroll 10-12 trauma-focused therapy (TFT) providers at the Minneapolis VAHCS. Providers will be asked to complete a 45-60-minute semi-structured interview during which they will provide their opinion on a draft version of a self-management intervention for Veterans who have completed TFTs. The interviews will be recorded and transcribed. We will use VHA administrative data to identify potential participants.

Providers will be eligible to participate in the interviews if (a) they provided a TFT to at least four Veterans during the past twelve months and (b) are staff providers (e.g. not trainees).

Aim 2. We will enroll 12 Veterans that seek care at either the Minneapolis VAHCS or Northwest Metro VA Clinic (Ramsey, MN), to participate in the post-TFT therapist-assisted self-management intervention. Veterans will be asked to participate in the self-management intervention, complete a brief survey at baseline (immediately prior to the first self-management session) and follow-up (12 weeks later), and participate in a 45minute semi-structured interview at the follow-up time point. While follow-up procedures are planned to be completed 12 weeks after a participant's first self-management session, there can be unforeseen scheduling and logistical conflicts that may push this timeline back. Provider and veteran can handle these circumstances on an individual basis and adjust the timeline as seen fit. Follow-up procedures should be completed with the goal of 12 weeks after the first self-management session but can be completed up to 16 weeks after the first self-management session if unable to stick to the original outlined study schedule. Veterans will be eligible to participate if they (a) are about to complete a course of individually-delivered TFT (enrollment will occur one to three weeks prior the final session or immediately before the final session) with a provider trained to deliver the self-management intervention, (b) experienced a clinically meaningful reduction in PTSD symptomology (PCL decrease of at least 10 points) from pre-TFT to the time of the enrollment, (c) at the time of enrollment are not planning to initiate another active course of psychotherapy for PTSD in the following three months, (d) are willing to participate in a self-management intervention, and (e) can provide informed consent. Veterans will be excluded if they have suicidal or homicidal ideation that in the opinion of their TFT therapist needs to be the focus of treatment. We will use a combination of provider referrals and administrative data to identify potential participants. We will also access VHA administrative data for surveyed Veterans in order to collect contact information, demographic characteristics, and mental health service utilization information.

2. Data Sources

The proposed project will use information that we gather through individual TFT provider interviews, Veteran surveys, individual Veteran interviews, audio recordings of the self-management sessions, and VHA administrative data. VHA administrative data will also be extracted to identify potential Veteran participants. The data will be gathered solely for research purposes.

3. Potential Risks

For both Aim 1 and Aim 2, the proposed research poses "minimal risk" to subjects as the risks are no greater than what are encountered in routine clinical care.

Aim 1 Risks: The primary risk to provider study participants is the potential loss of privacy and confidentiality; during the interviews, participants will be asked to provide their opinion on the self-management intervention, not their own personal experiences, so the consequences of a breach of privacy and/or confidentiality are believed to be negligible. There are no anticipated economic, physical, or social risks in this study.

Aim 2 Risks: The primary risk is the potential loss of privacy and confidentiality. The other potential risk associated is psychosocial stress resulting from either participation in the assessments or the intervention. The questionnaires and interviews will ask about current mental symptoms and functioning; the questions are consistent with those included in routine clinical care, and participants can refuse to answer any question(s). The self-management intervention may cause individuals to experience some psychological or social discomfort; however, we believe the intervention is likely to increase their well-being given that they are continuing to implement skills that they have already found to be helpful. The potential economic risks include potential loss of wages and transportation costs associated with traveling to and participating in the research intervention. There are no anticipated physical or social risks in this study.

Adequacy of Protection from Risks

1. Recruitment and Informed Consent

Provider Aim 1 Interview Recruitment & Consent: Eligible providers will be invited to participate in a 45 to 60-minute semi-structured interview via an e-mail from the principal investigator and will be able to either opt out of the study or to schedule an interview via e-mail. If providers do not respond to the initial e-mail, they will receive an additional e-mail and a follow-up phone call. If we fail to reach or receive a contact back from a provider after those contacts, we will assume they are not interested in participating in the study. We anticipate this activity will be IRB exempt and therefore will not include informed consent.

Veteran Aim 2 Recruitment & Consent: Veterans who meet eligibility criteria will be introduced to the study by their TFT provider. If participants agree to be contacted by the project, we will call participants to invite them to participate in the study. Veterans will receive three phone calls; if we fail to reach or receive a contact back from a Veteran after those contacts, we will assume they are not interested in participating in the study. Once we make contact with a Veteran, project staff will describe the purpose of the study and the risks and benefits associated with participating. Study staff will also administer a PTSD Checklist via the telephone to verify study eligibility. Veterans who are interested in participating in the study will meet in-person at the Minneapolis VA Medical Center or Northwest Metro VA Clinic with study staff one to three weeks before their final TFT session. If unable to complete during that timeframe, then informed consent will be completed immediately prior to their final TFT. If travel is burdensome or Veteran is unable to meet in person, then the Veteran can be mailed a consent form and HIPAA to be returned to staff prior to beginning the self-management intervention sessions.

2. Protection Against Risk

For both Aim 1 and Aim 2, the proposed research poses "minimal risk" to subjects as the risks are no greater than are encountered in routine clinical care. The potential risks to study participants include loss of privacy and confidentiality, psychosocial stress (any research project with direct contact with human subjects contains some risk of deleterious effects due to psychosocial stress), and loss of wages / transportation costs associated with study participation. There are no known physical or social risks of participating in the study. CCDOR has well-established methods to limit the risk of loss of confidentiality and protect the privacy of research participants.

The following procedures will be employed to ensure privacy and confidentiality:

Interviews & Session Audio-recordings:

- 1. Participants will be assigned a pseudonym identifier to be used instead of actual names in the audit trail, interview transcripts, and interview labels.
- 2. The only copy of the key linking actual names to pseudonyms will be kept in a password protected file, stored on a secure server.
- 3. Other individuals referred to by participants during the interviews will not be referenced by name in the study materials but only by salient but non-identifiable characteristics.
- 4. All electronic recordings, interview transcripts, and analytic notes will be stored in VA servers.
- 5. Handwritten notes will be stored in a locked cabinet in [name] VA office.
- 6. At the conclusion of the study, data will be destroyed in accordance with VA policy.

Survey Data:

- 1. Veteran contact information will be stored in a SQL server database. A study identification number (StID) will be pre-printed onto the survey so Veterans" identifying information remains private while maintaining the ability to link the survey back to an individual.
- 2. The data analyst will construct SAS datasets for analyses. All PHI will be removed from the SAS files, and a StID will serve as the only key to the initial data files. The programmer will have the only access to a crosswalk file linking StIDs with securely stored initial data files. Once the period for the required data maintenance has expired, all data will be destroyed under the supervision of the PI.
- 3. Our DART request will include permission to transfer necessary data to a local server to facilitate subject recruitment for Aim 1. We will create a separate workspace on a local server accessible only to the project programmers/data managers to process CDW abstracted data necessary for identification and recruitment of eligible subjects. The CCDOR Core Data Group works with OIT staff to maintain permission, data storage, and

server applications. All individuals with server access privileges have clearance to work with PHI. Backups are written to secured tapes and data stored in password protected project folders.

The CCDOR Statistical and Data Management (SDM) team maintain several secure servers accessible only SDM team members who have been screened and obtained proper security clearance. One common-access server contains individual project data. Access to that data is granted only through authorization by the principal investigator. Other VA investigators have used these procedures in previous studies and they have proved both feasible to execute and acceptable to multiple IRBs.

The second possible risk is distress among participants. While this risk is unlikely, we will take several steps to minimize this risk. Participants will be informed that participation is voluntary, that they may choose not to answer any questions and that they may discontinue their participation at any time. Further, we will provide participants with the Principal Investigator's (Pl's) phone number so that participants can contact [name] with any questions or concerns. The Pl is a licensed clinical psychologist with extensive experience working with Veterans with PTSD. Finally, if any study activities cause psychological distress or a psychiatric emergency emerges among participants, [name] will assess risk and provide appropriate referrals. All surveys will be screened upon receipt by study staff. If a psychiatric emergency is reported on surveys (i.e., expression of risk for suicide or homicide), [name] or [name] will contact the disclosing participant by phone, assess risk and safety, and provide the participant with appropriate referrals. We will utilize access to local and national mental health resources available through the VA, including the suicide prevention hotline, risk assessments through Mental Health during regular business hours (Psychiatry Urgent Care), or the facility's Emergency Room during off hours.

The final risk is economic. Participants may choose to take time off work or may incur transportation costs as a result of participating in this study. Every effort will be taken to schedule assessments and therapy sessions at times convenient to participants.

All collaborators will have completed appropriate human subjects trainings in the areas of research ethics and protection of human subjects.

Potential Benefits of the Proposed Research to the Subject and Others

There are no direct benefits to participation, although Veterans will receive \$20 for completing the Aim 2 baseline surveys; \$20 for completing the Aim 2 follow-up surveys; and \$25 for completing the Aim 2 semi-structured interviews. Thus, Aim 2 Veteran participants can receive up to \$65 for participation. Some participants may find it interesting to share their opinions. The knowledge to be gained during the course of this study may positively impact Veterans with PTSD's health and well-being.

Importance of Knowledge to be Gained

Most Veterans who complete trauma-focused therapies (TFTs) for PTSD continue to seek mental health treatment; however, therapists are providing these services without the benefit of evidence regarding effective post-TFT care. The VA / Department of Defense (DoD) PTSD Clinical Practice Guidelines recommend that Veterans who demonstrate a full remission of symptoms and improvement in functioning following TFT should discontinue psychotherapy, and those who experience a partial response should decrease the frequency and intensity of care (e.g. step-down). However, the guidelines do not provide recommendations for how to effectively reduce care in a manner that is acceptable to Veterans and maintains treatment gains. This project has the potential to improve the health and well-being of Veterans with PTSD and move the field forward by refining and evaluating the first intervention designed to help Veterans step-down from active to maintenance mental health services following a successful course of psychotherapy. Further, the project will advance RR&Ds missions of evaluating interventions designed to maximize psychological recovery and prioritizing functional outcomes and societal engagement.

Data and Safety Monitoring Plan

Privacy protections: All study data will be stored on CCDOR's secure data servers. CCDOR protects data collected for the purpose of conducting research projects at a level higher than that provided for clinical

encounters. We use "stand-alone," secure data servers that are accessible only to designated, security-cleared, and trained personnel and data are de-identified as quickly as is feasible. Details about CCDOR's specific data privacy assurance procedures to be employed for this study are provided below.

Maintaining Secure Servers: CCDOR maintains three secure computer servers that are protected under the Minneapolis VAMC Windows 2000 network. All individuals with administrative access privileges to the Center's servers, including IRM personnel and the CCDOR SDM Team, have been screened and assigned a security clearance putting them in trusted positions of the hospital with clearances to work with patient level data. These individuals and their access to the CCDOR servers is ultimately monitored and controlled by [name], Senior Program Analyst for the CCDOR Statistical & Data Management Team. IRM's access to the data is strictly limited to backing up server data, which prevents catastrophic loss of data. Backups are written to tapes that are stored in a secure location accessible only to IRM personnel. CCDOR's Statistical & Data Management Team members maintain permissions, data storage, and all server applications.

Organization and Access to Research Data: With the exception of one server, named the "CCDOR Server," only the CCDOR Statistical & Data Management Team has access to remaining Center servers. Data on the "CCDOR Server" are organized by projects within folders designated by each investigator. Only members of a given project have access to a specific project folder on the "CCDOR Server." Even then, access to project data is obtained through Windows authentication (i.e., PIV card). It is virtually impossible for any person without a login name and password to the VAHCS hospital's domain network to access data on the Center's servers. Thus, all data housed on the "CCDOR Server" is extremely secure, and access by unauthorized persons highly unlikely.

Securing Confidential Research Data: Primary data (e.g. interviews transcripts and survey responses) are identified only by participant number. The original data sources (e.g. digital recordings and paper notes) will either be kept in locked cabinets within a locked room or stored in a secure folder stored on the CCDOR server. Only individuals with a need to access the data, as vetted by the project's Principal Investigator are granted access. Even then, only the absolute minimum number of data elements is released. This protects the integrity of the data as well as its confidentiality.

Inclusion of Women and Minorities

Women and minorities will be represented in our study sample; all Veterans who complete TFT at the Minneapolis VAHCS who meet our inclusion criteria are eligible to participate. We will purposively sample women Veterans, with the goal of recruiting at least two women for Aim 2 activities. We will not purposively sample for race / ethnicity, but we anticipate that our sample will reflect the demographics of the population; given the demographic makeup of the Minneapolis VAHCS (82% White, 10% African American or Black; 3% Hispanic in the outpatient PTSD treatment program), we anticipate the majority of our sample will be White.

Inclusion of Children

All study subjects are expected to be 18 years of age or older.

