TFTs is bolstered by our prior work examining post-TFT treatment needs (Section 2A.3.1). The overall objectives of the therapist-assisted self-management program are to increase Veterans' self-efficacy for managing their PTSD, enable the maintenance or building upon gains made in TFT (e.g. formalize the expectation for continued practice of TFT skills and provide structure for the ongoing use of skills), and encourage engagement in meaningful activities. The program's components, the element of effective SM

programs
addressed by each
component, and the
specific goals
associated with the
components are
outlined in Table 2
(strategies that will
be employed within
each component
are expanded upon
in the detailed
outline of the
intervention

Table 3. Self-Management Intervention & Assessment Schedule

	Weeks Since Final TFT Session												
Self-Management Sessions	0	1	2	3	4	5	6	7	8	9	10	11	12
In-person session	Χ				Χ								
Phone check in			Χ										
Phone session											Х		
Assessment Schedule													
Baseline survey	Χ												
Follow-up survey													Х
Follow-up interview													Х

included in the Appendix). TFT therapists will assist Veterans with tailoring their plan to reflect their goals,

strengths, and the TFT completed (*PE and CPT modules will be available for components that require TFT-specific content; e.g. continued practice of TFT skills*). The draft program proposes four planned therapist contacts over the ten weeks following TFT completion (Table 3). Specifically, TFT therapists will meet with Veterans in person or through V-tel at the conclusion of TFT (SM intervention introduced during an expanded final TFT session), by phone for a brief check in two weeks after TFT completion, in person or through V-tel approximately four weeks after TFT completion, and by phone ten weeks after TFT completion. Therapists will also be available for additional contact as needed by Veterans; however, as *Veterans gradually develop greater self-efficacy in managing their PTSD symptoms, their need for therapist contact should decrease. Intervention development and refinement is ongoing and will continue until immediately prior to the Aim 2 therapist training.*

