2A.4.2. Aim 2 (Conduct a pilot open trial to assess the (a) acceptability of the SM program and (b) feasibility of SM program and the study approach) and Aim 3 (Explore the effects of the SM program) methodology. Sample Identification and Recruitment. Participants will be twelve Veterans at the Minneapolis VAHCS or Northwest Metro VA Clinic who experienced a clinically-significant improvement in PTSD symptomology (e.g., a decrease of at least 10 points on the PCL) following a course of individually-delivered TFT with a provider trained to deliver the SM intervention (study therapist). While the Stage Model of Treatment Development does not recommend a sample size for stage 1B activities, published accounts of psychotherapy treatment development frequently report on samples of ten to twelve participants. 48-51 Potential participants will be identified via referrals from study therapists; study therapists will refer their own patients to whom they will then deliver the intervention. To facilitate this process, we will identify potential participants via administrative data and notify study therapists that they are treating a Veteran who may be eligible for the study. We will first identify potential participants using the method described in Aim 1 Sample Identification (identification of Veterans who received an individual psychotherapy session for full or subthreshold PTSD and who have health factor data indicative of TFT delivery by one of the study therapists). Veterans who have attended at least six PE or eight CPT sessions (e.g., those nearing treatment completion as Veterans will be enrolled in the study immediately prior to treatment completion) will be selected for manual chart review, which will be used to confirm TFT delivery and verify additional inclusion criteria. Study therapists will introduce potential participants to the study: with the Veterans' permission, study staff will then contact him/her to describe the project in greater detail and ensure eligibility. Participants will complete informed consent with study staff one to three weeks before their final TFT session. If unable to complete during that timeframe, then informed consent will be completed immediately prior to their final TFT session. In some instances, Veterans may be mailed consent form and HIPAA to be returned to staff prior to first self-management

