framework.⁴⁴ The interviews will assess Veterans' (1) attitudes regarding the components (e.g. intervention targets), structure (e.g. level of therapist contact), and materials (e.g. handouts) of the intervention, (2) suggestions for improving the acceptability and efficacy of the SM program, (3) engagement with the SM program and materials (including retention), and perceived barriers/facilitators to engaging with the program, (4) perceptions of the impact of the program on the intervention targets (e.g. self-efficacy, outcomes associated with improved self-management) and exploration of unexpected domains impacted by the program, and (5) the completeness and time burden of the survey battery. Veterans will be paid \$25 for completing the interview. We will also extract the following administrative data: (1) the number of SM sessions attended by each Veteran (from electronic medical record; retention), (2) SM program fidelity ratings (see Fidelity Assessment above), (3) the number of "as-needed" contacts between Veterans and study therapists (from the electronic medical record; intervention fidelity), (4) the number of participants screened each month (screening), and (5) the number of eligible Veterans who declined participation (recruitment).

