Data Analysis. To assess the acceptability of the treatment program, we will calculate the percentage of participants who report neutral or better treatment credibility and expectancy on the Credibility-Expectancy scale and examine the distribution of scores on the Client Satisfaction Scale. We will triangulate these quantitative data with qualitative themes related to acceptability (qualitative data will be analyzed using the same methodology as described in Aim 1 Data Analysis); specifically, we will create a matrix with themes that emerge from the interviews regarding the programs' acceptability stratified by Veterans' quantitative Credibility-Expectancy and Satisfaction scores. Qualitative themes regarding the feasibility domain of program retention will be triangulated with administrative data regarding session attendance; a matrix presenting themes associated with high, medium, and low attendance (tertiles) will be produced by [name]. Descriptive statistics and graphical representations depicting intervention fidelity, screening, and retention will be generated. To assess the feasibility of the assessment approach, we will calculate rates of survey non-response and item missingness. We will also create a matrix summarizing themes related to the assessment process. Finally, we will calculate and graphically display the direction and magnitude of change from baseline

to follow-up for self-efficacy and outcomes associated with improved SM; we will also calculate the percentage of participants who improved, worsened, and experienced no change for each of these measures. These quantitative data will be triangulated with qualitative themes regarding self-efficacy and other program-related outcomes; themes and exemplary quotations will be presented in a matrix stratified by self-reported change (improved, worsened, no change) on the survey measures. We will also calculate descriptive statistics and pre-to-post treatment effect sizes for the sample.

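### Does the lack of a cut-off for improved, worsened and no change undermine the Aim 3 results?

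*Combined protocol and SAP*

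**What the plan says.** Section 2A.4.2, Data Analysis, plans several views of change between the baseline and follow-up surveys. The team will "calculate and graphically display the direction and magnitude of change from baseline" to follow-up for self-efficacy and the outcomes. Then "we will also calculate the percentage of participants who improved, worsened, and experienced no change for each of these measures". Themes and quotations from the interviews are to be "presented in a matrix stratified by self-reported change (improved, worsened, no change) on the survey measures". The paragraph ends with descriptive statistics and pre-to-post effect sizes for the sample.

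No cut-off, tolerance or reliable-change rule for the three classes appears anywhere. The only change value in the documents is 10 PCL points, and it serves eligibility: a Veteran must have "experienced a clinically meaningful reduction in PTSD symptomology (PCL decrease of at least 10 points) from pre-TFT to the time of the enrollment" (Human Subjects, Aim 2). Section 2A.4.1 (Self-Management Intervention) lists among the program's objectives to "enable the maintenance or building upon gains made in TFT".

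**The concern.** The program helps Veterans step down from TFT, so a stable score is one of its intended results, and *no change* is the class that ought to hold it. The sentence that names the classes also speaks of direction of change and mentions no threshold, so a reader may assume that the sign of the change decides the class. A 1-point rise on the PCL would then count as worsened.

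On that reading, about half of a group that kept its gains would be reported as worse, and the quotations of stable Veterans would be split by measurement noise between two opposite columns of the matrix. The results are meant to support an application for a randomized trial, so a misleading percentage could carry forward. A cut-off chosen after the data are seen would raise a different worry.

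**Working it through.** The plan states no figure for the classes, and the sample of 12 rests on precedent, so there is no planned number to reproduce. The check asks how the classes would behave under each rule.

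**Inputs.** From the documents: n = 12, and 10 PCL points as the entry criterion. Assumed: change (follow-up minus baseline; a rise is worse) is normal, rounded to whole points, with mean μ and SD σ of 6 to 12; all 12 are followed up. Φ is the standard normal distribution function.

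**1. Direction only, μ = 0.**

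- P(no change) = Φ(0.5/σ) − Φ(−0.5/σ)
- P(worsened) = 1 − Φ(0.5/σ)
- P(*no change* empty) = (1 − P(no change))^12

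| σ | No change | Expected of 12 | Worsened | *No change* empty |
|---|---|---|---|---|
| 6 | 6.6% | 0.8 | 46.7% | 44% |
| 8 | 5.0% | 0.6 | 47.5% | 54% |
| 10 | 4.0% | 0.5 | 48.0% | 61% |
| 12 | 3.3% | 0.4 | 48.3% | 67% |

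Of those labelled worsened, 56% (σ = 12) to 88% (σ = 6) rose by only 1 to 9 points. On this reading the worry is real for the PCL. On a generic short scale (assumed σ of 2 to 4) the unchanged share is 10% to 20%, so the effect is weaker there.

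**2. The obvious remedy: no change means less than 10 points either way.**

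- P(no change) = Φ((9.5 − μ)/σ) − Φ((−9.5 − μ)/σ)
- P(worsened) = w = 1 − Φ((9.5 − μ)/σ)
- For μ = 0, P(improved or worsened empty) = 2(1 − w)^12 − (1 − 2w)^12

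| σ (μ = 0) | No change | Worsened | Improved or worsened empty |
|---|---|---|---|
| 6 | 88.7% | 5.7% | 76% |
| 8 | 76.5% | 11.8% | 41% |
| 10 | 65.8% | 17.1% | 20% |
| 12 | 57.1% | 21.4% | 11% |

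The band fills *no change* but often empties one of the other two strata.

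**3. What the band hides.** A Veteran admitted on a gain of exactly 10 points could lose 9 of them and still be unchanged. With μ = 8, the share labelled worsened is 1 − Φ(1.5/6) = 40% at σ = 6 and 1 − Φ(1.5/12) = 45% at σ = 12. In a group that had on average lost most of a minimum entry gain, fewer than half would be called worsened. The band does not identify maintenance reliably either.

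**4. Scope.** The table of outcome domains in section 2A.4.2 (Data Collection) gives eight change measures, and the PCL is one. The documents offer no threshold for the other seven, so a PCL band would leave them as they are.

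**5. What is displayed anyway.** The magnitude display shows a 1-point rise as a 1-point rise under any class rule. The mean change and effect size for a stable group would be expected near zero.

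**The case for a change.** The strongest argument for a change is that the same paragraph does give a rule for its other groupings: neutral or better for treatment credibility and expectancy, tertiles for session attendance. Only the change classes lack one. The magnitude display also does not repair the matrix, where noise would still sort the quotations. Stating a rule in advance costs a few sentences.

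Part of this stands. The gap is in the text, and choosing the rule for each measure before follow-up data are seen, with each Veteran's change printed beside the class, would be good practice. But this is ordinary analyst's work. The text names direction and magnitude together and treats *no change* as a stratum of its own, which fits a tolerance still to be set as well as it fits direction alone. The matrix also rests on interviews that ask each Veteran directly about the program's impact, so a stable Veteran's account remains readable whichever column holds it.

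A related complaint is that follow-up is not set against the pre-TFT PCL, which is missing from the list introduced by "We will also extract the following administrative data" (section 2A.4.2, Data Collection). That list covers retention, fidelity, screening and recruitment. The pre-TFT score is needed for the entry criterion in any case, and at recruitment "Study staff will also administer a PTSD Checklist via the telephone to verify study eligibility". Its absence from the list does not show that it is unavailable, and it does not enter the baseline-to-follow-up classes. Selection on a fall since pre-TFT can bring regression to the mean, but with independent measurement errors this does not affect the change from baseline survey to follow-up.

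**Conclusion.** No change to the plan is needed. The three classes are undefined, and a sign-only rule would serve the PCL poorly: 3% to 7% unchanged and 47% to 48% worsened in a stable group. Those figures depend on an inferred rule, an assumed SD of 6 to 12 points and a normal model with mean zero; floor effects in treatment responders, which could produce more exact ties, were not examined.

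The consequence is small even on that reading. Aim 3 is exploratory, with one arm and 12 Veterans; no decision rule uses the classes; and the planned magnitudes, effect sizes and interviews would show whether gains were kept. A 10-point band is a trade-off, not a correction. It leaves the improved or the worsened stratum empty in 11% to 76% of such pilots and misses most of a true mean rise of 8 points. The analysts can settle the class rule sensibly within the plan as written.
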